4.4 Duration of Therapy

Therapy with furosemide will continue daily for 5 days unless there is the development of intercurrent illness that prevents further administration of treatment, unacceptable adverse events, patient withdrawal from the study, or general or specific changes in the patient's condition render continued treatment unacceptable.

4.5 Duration of Follow Up

Patients will be followed for 10 days after discharge. All patients that consent to the study will be expected to enroll at an established program at the Hospital of the University of Pennsylvania to monitor blood pressures postpartum through daily texting. Patients will be expected to measure their blood pressures at least once daily and text them to a physician through the program. The program, Heart Safe Motherhood, has been utilized successfully over the past year to follow-up women after discharge and be more readily available to monitor blood pressures and give advice. Patients removed from treatment for unacceptable adverse events will be followed until resolution or stabilization of the adverse event.

4.6 Removal of Patients from Protocol Therapy

Patients will be removed from therapy when any of the criteria listed in Section 4.2 and 5.5 apply. The Principal Investigator will be notified and document the reason for study removal and the date the patient was removed in the Case Report Form. The patient will be followed-up per protocol.

4.7 Management of blinding

This is a double blind study and therefore physicians, staff, and patients will be blinded to the patient's allocated treatment group. In the event of a potential suspected unexpected serious adverse reaction, unblinding will be undertaken by the PI. Unblinding may also be performed at the request of a senior clinician responsible for the care of a trial participant but such requests are likely to occur only in the case of an adverse clinical event and are expected to be rare. Any request to unblind treatment allocation for clinical reasons will be made directly to IDS and the treatment allocation will be reported to the relevant clinician. The PI and main trial manager will be kept informed of all instances of unblinding but remain blind to treatment allocations themselves wherever possible. All requests for unblinding will be recorded by research staff and IDS.

5 STUDY PROCEDURES

5.1 Screening for Recruitment and Recruitment Process

The labor and delivery board and patient list will be screened daily to identify eligible patients. Women identified as having a hypertensive disorder of pregnancy will be invited to participate in the study and written informed consent will be obtained from those who choose to participate in the postpartum period. All screening procedures must be performed within 24 hours of delivery. The screening procedures include:

5.1.1 Informed Consent

5.1.2 Medical history

Complete medical and surgical history

5.1.3 Demographics

Age, gender, race, ethnicity

5.1.4 Review subject eligibility criteria

5.1.5 Review previous and concomitant medications

5.1.6 Physical exam including vital signs, height and weight

Vital signs (temperature, pulse, respirations, blood pressure), height, weight

5.1.7 Adverse event assessment

Baseline adverse events will be assessed. See section 6 for Adverse Event monitoring and reporting.

5.2 Randomization

If the patient is eligible, after informed consent the patient will be randomized by IDS. We plan to randomize through a computer generated sequence in blocks of 4 and stratify randomization blocks by whether severe features are present or not (ie., gestational hypertension and pre-eclampsia without severe features vs. pre-eclampsia with severe features). IDS will then dispense the furosemide or placebo accordingly.

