1.2 Study Agent(s)/Devices Background and Associated Known Toxicities

Furosemide (Lasix) is a loop diuretic that is also a known antihypertensive. It exerts its mechanism of action by inhibiting reabsorption of sodium and chloride in the ascending loop of Henle and distal renal tubule. It also interferes with the chloride-binding cotransport system. Accordingly, this causes increased excretion of water, sodium, chloride, magnesium, and calcium. It is known to have onset of action of up to 60 minutes if given by mouth and 5 minutes if given by IV for diuresis. Duration is estimated to 6-8 hours when given orally and 2 hours when given IV. It is a hepatically metabolized medication with 91-99% protein binding (mostly albumin). Bioavailability ranges from 47-64% orally and it has a half-life of 0.5–2 hours. Excretion is through the urine with 50% of the PO version 80% of the IV version of the drug excreted within 24 hours. Significant side effects are related to the fluid and electrolyte shifts that occur with its lack of resorption of electrolytes. These include, but are not completely limited to ototoxicity, mood changes, confusion, muscle pain, palpitations, dizziness, syncope, increased thirst, fatigue, weakness, decreased appetite, dry mouth, dry eyes, upset stomach, nausea, and emesis.

Prior studies for the prevention and treatment of postpartum hypertension with furosemide had mixed results. Three trials (390 women) assessed oral furosemide (20-40 mg/day) in postpartum women with preeclampsia.³ In one study, there was a non-statistically significant trend to more rapid blood pressure reduction in the group receiving furosemide.¹⁴ The second study showed that furosemide, given postpartum, was associated with reduced systolic blood pressures only among women with severe preeclampsia.¹⁵ Meanwhile, the third study found that although furosemide was able to reduce the amount of antihypertensive medication given, no significant differences in

blood pressures were found in patients with severe preeclampsia. Given the inconclusive results and little data thus far on the use of postpartum furosemide, a recent Cochrane review concluded that more data is needed on substantive outcomes before the practice of postnatal furosemide can be recommended.

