Placebo will be given to half of our enrolled patients which will be determined through randomization. All placebo will be manufactured and distributed by the Investigational Drug Service (IDS) of the University of Pennsylvania. IDS will manufacture the placebo to be similar to the furosemide pill. If necessary, IDS will add a coating shell to both the furosemide and placebo pills to ensure that all pills look similar.

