3.2 Exclusion Criteria

- **3.2.1** History of allergic reaction to furosemide
- 3.2.2 High risk comorbidities for which treatment may be indicated or contraindicated: class C or higher diabetes mellitus, chronic kidney disease or baseline creatinine >1.2, cardiac disorders including cardiomyopathy, congenital heart disease, angina or coronary heart disease, rheumatic disease (lupus), sickle cell disease
- 3.2.3 Baseline labs with K <3
- 3.2.4 Use of furosemide or other diuretics antepartum or intrapartum
- **3.2.5** Use of ototoxic agents including aminoglycosides (ie, Gentamicin for >1 dose), cephalosporins (ie Ancef >1 dose),
- **3.2.6** Patient unstable for protocol per investigator's judgement

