4.2 Toxicities and Dosing Delays/Dose Modifications

Any patient who receives treatment will be evaluable for toxicity. Each patient will be assessed for the development of toxicity according to development of ototoxicity or symptomatic derangements in electrolytes as determined by symptoms and corresponding daily basic metabolic profiles. In the event of the development of either, the medication will be discontinued.

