Patients in both groups will undergo similar postpartum surveillance, including blood pressure and pulse assessment every 4 hours and urinary output measurements while hospitalized. Proper treatment for elevated blood pressures will be initiated immediately as soon as the elevated blood pressures are recognized, and will not be delayed for any study purposes including study drug administration. For this study, antihypertensive therapy will be initiated for persistently elevated postpartum blood pressures (BP) of ≥ 150 systolic or >100 mg Hg diastolic with 5 mg of amlodipine PO. Persistent severe range blood pressures (BP >160 mm Hg systolic or >110 mm Hg diastolic) will be treated with IV antihypertensives if needed, as well as 10 mg of amlodipine PO. If further antihypertensive medications are needed to maintain blood pressures <150/100, these will be per the discretion of the clinical staff in both arms. All physicians and clinical staff in Labor and Delivery as well the postpartum unit will be educated extensively to avoid diuretic antihypertensive medications unless deemed medically necessary. Furthermore, diagnostic and laboratory tests will be per the discretion of the clinical staff in both arms as well. Routinely, all patients undergoing cesarean section remain hospitalized for at least 3 days and all patients with preeclampsia with severe features are kept in the hospital for 3 days (per the recommendations of the ACOG Task Force on Hypertension in Pregnancy). 10 All patients will be followed at for 10 days after discharge as detailed below. Being enrolled in the study will not change the patient's clinical care at any time. Physicians, staff, and patients will be blinded to the intervention administered, unless a break in blinding is required for medical intervention of adverse effects.

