9 STUDY DESIGN/STUDY ENDPOINTS

This will be a prospective, randomized, double-blinded, single center study of the impact of a short course of furosemide on postpartum blood pressure recovery in women with hypertensive disorders of pregnancy (HDP). Please refer to Section 2.4 for end points.

Regarding stopping rules for safety or efficacy, we do not anticipate early termination of the study for either. Issues that would be of concern would be persistent hypokalemia (< 3.0) with therapy, ineffectiveness of therapy (as defined by the use of the same dosing of other antihypertensive agents for blood pressure control), and unexpected events (admission to ICU). Other findings that could trigger a safety review include the number of SAEs overall, the number of occurrences of a particular type of SAE, severe AEs, or increased frequency of events.

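### A single stated block size of 4 at one centre leaves a residual route to predicting allocations; varying, undisclosed sizes would remove nearly all certain predictions at little cost

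*Combined protocol and SAP*

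**What the plan says.** Section 5.2 gives one block size: the plan is to "randomize through a computer generated sequence in blocks of 4" and to "stratify randomization blocks by whether severe features are present or not". Staff caring for the women will normally know the stratum, because it is the clinical diagnosis. Allocation is 1:1 (section 1.2: "Placebo will be given to half of our enrolled patients"), so each block holds two women per arm. Section 9 describes a "prospective, randomized, double-blinded, single center study", so one group of staff can see the whole enrolment sequence of each stratum.

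Section 5.3 has both groups undergo "urinary output measurements while hospitalized". Section 1.2 says of the drug's diuretic effect: "Duration is estimated to 6-8 hours when given orally". Section 4.2 also refers to "corresponding daily basic metabolic profiles" when describing how toxicity is assessed.

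Several safeguards are written in. IDS randomizes after eligibility and consent (5.2, 5.3), capsules are over-encapsulated and visually matched (8.1.1), and physicians, staff and patients are blinded (4.7). Nowhere does the plan vary the block size, withhold it from recruiting or ward staff, or provide for a check of blinding.

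**The concern.** Matching capsules hide the appearance of the drug but not its action. If charted urine output gives even a partial clue to the arm of women already enrolled, a known block size converts those clues into a forecast for the next woman in that stratum.

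Two things could then be affected. The first is selection. Staff decide whom to approach and when, and section 3.2 contains a discretionary exclusion, "Patient unstable for protocol per investigator's judgement", which is applied before randomization. The second is treatment after randomization. A need for additional antihypertensives meets the primary composite by itself (2.3.1), and agents beyond amlodipine are left to clinical staff (5.3).

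Pace makes the first route feasible. If 385 women enrol evenly over the stated 20 months and split equally between strata (both assumptions), each stratum enrols 385 / 20 / 2 = 9.6 women a month, about one every 3 days. The effect of a first dose could be charted before the next woman in that stratum is enrolled.

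**Working it through.** The plan gives no figure for predictability, so there is none to reproduce.

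**Inputs.** Block size 4 and two strata (5.2); 1:1 allocation (1.2); 385 randomized (9.1). The probability *q* that staff infer a past arm correctly is an assumption. It runs from 0.5 (no information) to 1 (perfect).

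**Fixed blocks of 4, perfect inference.** There are 6 equally likely sequences of two and two. The guesser picks the arm with more places left in the block.
- Position 1: correct with probability 1/2.
- Position 2: 2/3.
- Position 3: the first two match with probability 1/3 (then certain), otherwise it is even: 1/3 × 1 + 2/3 × 1/2 = 2/3.
- Position 4: 1.

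Mean accuracy = (1/2 + 2/3 + 2/3 + 1) / 4 = 17/24 = 70.8%. Certain allocations = (1/3 + 1) / 4 = 33.3%, or about 128 of 385.

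**Fixed blocks of 4, imperfect inference.** Weight each of the 6 sequences by *q* for every agreement with the inferred arms and 1 − *q* for every disagreement, then guess the likelier arm. Accuracy by position is 1/2, (1 + *q*)/3, (1 + *q*)/3 and 2*q* − 3*q*² + 2*q*³. At *q* = 0.8 this is (0.5 + 0.6 + 0.6 + 0.704) / 4 = 60.1%. At *q* = 0.7 it is (0.5 + 0.567 + 0.567 + 0.616) / 4 = 56.2%. No allocation is certain when *q* is below 1.

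**Sizes 4, 6 and 8 drawn at random.** The comparison must use an equally able guesser, so this one knows the set of sizes, does not know the current size, and updates by Bayes' rule after each woman. These values are simulated.

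| Assumed *q* | Fixed 4 | Varying 4/6/8 |
|---|---|---|
| 0.5 | 50.0% | 50.0% |
| 0.6 | 53.0% | about 52% |
| 0.7 | 56.2% | about 54% |
| 0.8 | 60.1% | about 56 to 57% |
| 0.9 | 64.9% | about 60% |
| 1.0 | 70.8% | about 68% |
| Certain allocations at *q* = 1 | 33.3% | about 2% |

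The average gain is 1 to 4 points at 60%, 70%, 80% and perfect inference, and nearly 5 at 90%. The large change is in certain predictions.

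**Cost in balance.** The largest imbalance from an unfinished last block is half the block: 2 women per stratum with blocks of 4, and 4 with a block of 8.

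**The case against.** The best case for leaving section 5.2 alone is that the premise is unproven and the safeguards are real. The dose is 20 mg orally once a day, section 1.3 describes large postpartum fluid shifts that would affect both arms, and open-label furosemide is allowed when medically necessary (4.3). Urine output may therefore be a noisy marker. To exploit block position, someone would have to infer arms from ward charts, track enrolment order within each stratum and get that to the person recruiting. The protocol describes no such channel. Starting amlodipine depends on blood-pressure thresholds and applies regardless of arm (4.3), so staff expectation has limited room to move the primary composite. Fixed blocks of 4 are also a conventional choice that keeps the strata balanced.

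Most of this stands, and it sets the weight of the point. It does not remove the point, because nothing in the plan hides or varies the block size.

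Three stronger readings are tempting, and the documents support none of them:
- That a third of allocations are known in advance. This needs every past arm in the stratum to be known, which the blinding is there to prevent.
- That varying the blocks would cut guessing from 71% to 63%. The 63% belongs to a simple recent-balance guesser, whereas the 71% belongs to an optimal one. Like for like, it is 71% against 68%.
- That the change would protect the endpoint from unmasking in general. A clinician who infers a woman's arm from her own urine output can do so under any block size.

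**Conclusion.** The point holds as a residual weakness of modest weight. Section 5.2 discloses one fixed block size for two recognizable strata at one centre, in a trial whose drug action leaves a charted trace. Predictability of the next allocation lies somewhere between 50% and 70.8%. The documents cannot place it more closely, because they give no information on how well urine output reveals the arm. The 56% and 60% figures rest on assumed inference rates of 70% and 80%, on independent inferences for each woman, and on staff knowing the block size and the order of enrolment. Varying sizes would mainly remove certain predictions, which are the ones most useful to anyone choosing whom to enrol. Nothing in the documents shows that allocation has been predicted or that enrolment has been biased.

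**What to change.** Consider three linked changes:
- Keep the two strata, and have IDS generate the list with block sizes drawn at random, for example from 4, 6 and 8.
- Record the sizes only in a document held by IDS.
- In section 5.2, replace the stated size with wording such as *in permuted blocks of varying size*.

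Urine-output measurement stays as it is. The work is one regenerated computer list and one changed phrase, with no added patients, visits or procedures. The price is a worst-case final imbalance of 4 instead of 2 women per stratum (8 instead of 4 over both strata), which is small against 385.

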Furosemide for Accelerated Recovery of Blood Pressure Postpartum: a randomized controlled trial (FoR BP trial)

A randomized, double-blind, placebo-controlled single center investigation of furosemide's effect on postpartum blood pressure control in pregnancies affected by hypertensive disorders of pregnancy

Protocol date: July 19, 2018

NCT#03556761

Furosemide for Accelerated Recovery of Blood Pressure Postpartum: a randomized controlled trial (FoR BP trial)

A randomized, double-blind, placebo-controlled single center investigation of furosemide's effect on postpartum blood pressure control in pregnancies affected by hypertensive disorders of pregnancy

Principal Investigator: [name], MSCE

Assistant Professor

Division of Maternal Fetal Medicine

Department of Obstetrics and Gynecology

[name]

[name]

Sub-Investigator(s): [name] [name]

Clinical Fellow

Division of Maternal Fetal Medicine

Department of Obstetrics and Gynecology,

Study Drug/Study Device: Furosemide (Lasix)

LIST OF ABBREVIATIONS

AE Adverse Event

CTCAE Common Terminology Criteria for Adverse Events

DSMB Data and Safety Monitoring Board

gHTN Gestational hypertension H&P History & Physical Exam

HRPP Human Research Protections Program
HDP Hypertensive disorders of pregnancy

[figure not shown]
HTN Hypertension IV (or iv) Intravenously

PI Principal Investigator
PO per os/by mouth/orally
PPHTN Postpartum hypertension

PR Partial Response

SAE Serious Adverse Event

STUDY SCHEMA

STUDY SUMMARY

Title	Furosemide for Accelerated Recovery of Blood Pressure Postpartum: a randomized controlled trial			
Short Title	FoR BP trial			
Methodology	Double blind, randomized, placebo control design			
Study Duration	20 months			
Study Center(s)	Single-center			
Objectives	To investigate the impact of a short course of furosemide on postpartublood pressure recovery in women with hypertensive disorders of pregnancy (HDP).			
Number of Subjects	385			
Diagnosis and Main Inclusion Criteria	Clinical disease state under study: hypertensive disorder of pregnancy, postpartum with delivery >20 weeks EGA, diagnosis of HDP antepartum, intrapartum and up to within 1 day of delivery			
Study Product(s), Dose, Route, Regimen	Furosemide (Lasix), 20mg, PO, daily			
Duration of administration	5 days			
Reference therapy	Placebo			
Statistical Methodology	Intention to treat analysis, chi-square tests for categorical variables, two-sample t-test for continuous variables			

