2.3 Endpoints

2.3.1 Primary endpoint

- **2.3.1.1** Postpartum hypertension composite outcome, defined as:
 - Persistently elevated blood pressure (≥140/90) at 7 days postpartum OR
 - Additional requirement of antihypertensive agents after randomization

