9.1 Sample Size and Accrual

The sample size is based on a current ongoing study at HUP in which 45.6% of patients had persistently elevated blood pressures 7 days after delivery. For a power of 80% and a statistical significance level of 5%, 175 patients would be needed to find a 40% reduction in blood pressures with the use of furosemide. In anticipation of possible post-randomization losses of approximately 10% of patients, we plan to recruit 385 participants for randomization in the two groups.

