9.2 Data Analyses Plans

To account for the multiple measurements per patient, we will employ repeated measure regression techniques. Measures of relative risk will include 95% confidence intervals. Descriptive statistics will be presented as mean with standard deviation, median with interquartile range, or proportion with 95% confidence interval based on data type and distribution. Comparisons between groups will be performed using a Chi-square or Fisher's exact test for categorical variables and parametric or non-parametric tests for continuous variables, as appropriate. Bivariable analysis will be used to determine variables (risk factors) that are independently associated with PPHTN. Intention-to-treat analyses will be conducted such that all patients with available follow-up measures will be included in the analysis. Blood-pressure measurements after randomization will be compared between groups with the use of a mixed-effects logistic-regression model, which will account for participants having different numbers of observations over a varying time span. Statistical analyses were conducted in SAS, version 9.4 (SAS Institute, Cary, NC). Two-tailed P values of <0.05 will be considered statistically significant.

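### Randomisation is stratified by severe features, but no planned treatment comparison names the stratum; the unstratified chi-square test is valid but slightly conservative if the stratum is prognostic

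*Combined protocol and SAP*

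**What the plan says.** Section 5.2 uses a computer-generated sequence in blocks of 4 and will "stratify randomization blocks by whether severe features are present or not". The primary endpoint in 2.3.1 is a yes/no composite: elevated blood pressure at 7 days, or "Additional requirement of antihypertensive agents after randomization".

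The analysis text does not mention the stratum:

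- Study Summary: "chi-square tests for categorical variables".
- Section 9.2, group comparisons: "Comparisons between groups will be performed using a Chi-square or" Fisher's exact test for categorical variables.
- Section 9.2, effect measure: "Measures of relative risk will include 95% confidence intervals".
- Section 9.2, repeated readings: repeated-measures regression, and "Blood-pressure measurements after randomization will be compared between groups with the use of a mixed-effects logistic-regression model". No covariates are listed.
- Section 9.2, risk factors: "Bivariable analysis will be used to determine variables (risk factors) that are independently associated with PPHTN". This looks for predictors of the outcome and is not a treatment comparison. It lists no variables either.

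Section 9.1 takes its control rate from an ongoing local study in which "45.6% of patients had persistently elevated blood pressures 7 days after delivery".

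**The concern.** Blocking within strata makes the arms nearly equal in their mix of severe and non-severe disease. Differences in event rate between strata then contribute almost nothing to the difference between arms. An unstratified chi-square test still counts that between-stratum variation as noise, so its standard error is too large whenever the stratum predicts the outcome.

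The stakes are low. There is no bias and no added false-positive risk. What is lost is a little power and a little width in the confidence interval, and both could be recovered from data the trial already holds. Section 9.2 should also settle in advance whether the stratum is in the primary analysis. At present it is not named, which is different from being excluded.

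A secondary point concerns who belongs in which stratum. Section 5.2 places pre-eclampsia without severe features in the lower stratum, but the list in 3.1.1 does not include that diagnosis. Section 3.1.1 includes superimposed pre-eclampsia, grouped with severe features, but the parenthesis in 5.2 places it in neither stratum. Section 3.1.2 admits a new hypertensive disorder without naming types.

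**Working it through.** **Inputs from the documents.** Equal allocation (1.2); blocks of 4 by severe features (5.2); control rate 45.6%, stated for 7-day blood pressure only (9.1); 40% reduction, read as a relative risk (RR) of 0.60 (9.1); two-sided 5% (9.2). The 385 to be randomised equals 350 × 1.10, so the 175 in section 9.1 is taken as evaluable women per arm.

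**Assumptions.** The share with severe features is f = 0.5 (0.3 and 0.7 as sensitivity). The gap in control event rate between strata is d = 0, 10, 20 or 30 points. The RR is the same in both strata. The composite rate cannot be below the 7-day rate in the same women, so 60% is shown as well.

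**The plan's own figure.** For 45.6% against 27.36% (0.60 × 45.6%), the pooled-variance formula gives 108.1, so 109 per arm for 80% power, not 175. With 175 per arm, power for that effect is about 95%. The formula needs 173 per arm at RR 0.68, so RR 0.68 is roughly what 175 per arm detects with 80% power. Both effects are carried forward. The mismatch in 9.1 is a separate matter and does not affect this point.

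**Size of the test.** The within-stratum share of the outcome variance is

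VR = 1 − f(1 − f)d² / [p(1 − p)].

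For p = 0.456, f = 0.5, d = 0.20: VR = 1 − 0.25 × 0.04 / 0.2481 = 0.960. The null standard error is too wide by 1/√VR − 1, and the type I error is 2[1 − Φ(1.96/√VR)].

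| Gap (points) | Control rates, severe / not | VR | SE excess | Type I error |
|---|---|---|---|---|
| 0 | 45.6 / 45.6% | 1.000 | 0% | 5.0% |
| 10 | 50.6 / 40.6% | 0.990 | 0.5% | 4.9% |
| 20 | 55.6 / 35.6% | 0.960 | 2.1% | 4.5% |
| 30 | 60.6 / 30.6% | 0.909 | 4.9% | 4.0% |

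At a 60% overall rate the SE excess is 0, 0.5, 2.2 and 5.0%, with the same rounded type I errors. With 30% or 70% severe at 45.6%, it is 0, 0.4, 1.7 and 4.0%.

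**Power.** Power = Φ[(Δ − 1.96·SE₀)/SE_within]. Here Δ is the risk difference, and SE₀ is pooled overall for chi-square or pooled within strata for Cochran-Mantel-Haenszel (CMH). At 45.6% and f = 0.5:

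| Gap | RR 0.60, chi-square vs CMH | RR 0.68, chi-square vs CMH |
|---|---|---|
| 0 | 94.7 vs 94.7% | 80.4 vs 80.4% |
| 10 | 94.7 vs 94.8% | 80.5 vs 80.7% |
| 20 | 94.9 vs 95.2% | 80.8 vs 81.6% |
| 30 | 95.3 vs 95.9% | 81.3 vs 83.2% |

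The gain before rounding is 0, 0.1, 0.3 and 0.6 points at RR 0.60, and 0, 0.2, 0.8 and 1.8 points at RR 0.68. At a 60% control rate and RR 0.68 it is under 1 point. Expressed as women, 350 × (1 − within-stratum/total variance) at RR 0.68 and 45.6% is about 0, 3, 11 and 25.

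**Simulation.** 350 women, blocks of 4 within each stratum, 400,000 replicates, 45.6%, f = 0.5, gaps 0/10/20/30:

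| | Chi-square | CMH |
|---|---|---|
| No effect | 4.75 / 4.68 / 4.29 / 3.76% | 4.75 / 4.81 / 5.02 / 5.00% |
| RR 0.60 | 94.8 / 94.9 / 95.0 / 95.3% | 94.7 / 94.9 / 95.2 / 95.8% |
| RR 0.68 | 80.8 / 80.9 / 81.1 / 81.5% | 80.6 / 81.0 / 81.8 / 83.1% |

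A second simulation (1,000,000 null and 200,000 alternative replicates) agreed. Its gain at RR 0.68 and f = 0.5 was about 0.2, 0.6 and 1.4 points for gaps of 10, 20 and 30. At a 40-point gap the chi-square size fell to about 3.0% and the gain rose to about 3 points.

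**The case against.** The strongest reply is that nothing here would plausibly change the trial's conclusion. The planned test is valid. At the only effect the protocol states, the gain is at most 0.6 points from about 95% power. The larger figure of 1.8 points needs a relative risk of 0.68, which is not in the protocol, and a 30-point gap between strata, for which the documents offer no evidence. The background in 1.2 links severity to response to furosemide, not to baseline risk. All of this stands, and it is why the point is rated as low stakes.

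The simulated gains at RR 0.68 in the table (−0.2, 0.1, 0.7 and 1.6 points) are slightly below the formula's. The simulated chi-square size is already 4.75% with no gap, so part of that shortfall is discreteness and not the omitted stratum. That also stands, but the pattern is unchanged: CMH returns to about 5% as the gap grows, and chi-square does not.

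Section 9.2 does not assign a method to the composite by name, so the chi-square reading is an inference. It is the natural one for a single binary outcome per woman with no sparse cells, and the Study Summary supports it. The quantified loss applies only to that reading.

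Finally, the rule in 5.2, severe features present or not, can classify most women even where its parenthesis is silent. The membership point is therefore a secondary wording matter and should not raise the weight of the analysis point.

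**Conclusion.** The concern holds. The design stratifies by severe features and no planned treatment comparison names the stratum. The unstratified chi-square test keeps its error rate at or below 5%, and falls to about 4.0% at a 30-point gap between strata. The cost is at most 0.6 points of power at RR 0.60 and at most 1.8 at RR 0.68, by formula at a 45.6% control rate. If severe features do not predict the composite, the cost is zero.

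These sizes assume 175 evaluable women per arm, half with severe features, a common relative risk, and the 7-day rate standing in for the composite. A prognostic stratum is plausible, because blood pressure of 160/110 or more is one route into the severe group in 3.1.1, but the documents do not show it. This is a worthwhile specification improvement and does not threaten the trial's validity.

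**What to change.** In 9.2, name the primary analysis of the composite: one yes/no record per woman, CMH test, and Mantel-Haenszel relative risk with 95% confidence interval, stratified by severe features as recorded at randomisation. Modified Poisson regression with the stratum as a covariate is an acceptable alternative. This takes one or two sentences and no extra patients or data.

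Optionally, report stratum-specific relative risks as descriptive only, since 1.2 cites an earlier trial with an effect confined to severe disease. With 87.5 women per arm per stratum, a 20-point gap and RR 0.60, the 95% intervals would be about 0.42–0.85 (severe) and 0.37–0.98 (not severe) at 45.6%, or 0.45–0.80 and 0.41–0.88 at 60%. A Wald interaction test on the log relative risk, RR 0.60 against 1.00, would have 47% power if the effect were only in the severe stratum and 43% if only in the other (69% and 65% at 60%). No subgroup claim should rest on it.

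Separately, reconcile 5.2 with 3.1.1 and 3.1.2 so that each eligible diagnosis has a stated stratum. This needs a wording change in 5.2, 3.1 or both.
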